1.1 Introduction

Continual advancements in technology have dramatically changed the ways of surgical education. Multimedia-based technologies and different computer-based simulators have been studied to enhance the efficacy of training and to improve the quality of care by reducing surgical complications.^{1,2} The adoption of web technologies for cognitive online training can be a useful way of optimizing educational programs, allowing for anytime/anywhere training.³ Computer-based surgical simulation, including three-dimensional (3D) models and virtual reality (VR) immersive environments, also hold enormous potential in surgical education.⁴

Liver surgery is considered an essential part of the general surgery curriculum, and trainees in this field need guidance to learn the complex liver anatomy, pathophysiology, patient management and necessary operative skills to successfully manage patients. Despite the implementation of various training models to improve skills, there is currently absence of high-qualitative research that really demonstrates that training results in improvement of skills in the clinical setting.

1.2 Rationale and Objectives

In liver surgery, to perform safe and accurate hepatectomy, it is important to understand the complex liver anatomy and the relationship between the tumor and the intrahepatic structures. To date, preoperative assessment of patients with liver tumors have been

mainly reliant on Computerized Tomography scan (CT scan) and Magnetic Resonance (MR) images. These modalities are limited to 2D displays, which require surgeons to reconstruct 3D spatial images based on their clinical knowledge and experience. This process needs a vast cognitive knowledge of liver anatomy and pathophysiology, and possibly leads to a significant amount of cognitive load. Cognitive load refers to the amount of information being processed by the working memory resources at any point in time.^{5,6} To address this cognitive load in liver surgery, different desktop interface (DI) based 3D models and VR solutions have been developed.^{7,8} Evidence suggests that for experts 3D reconstruction is beneficial for planning complex liver surgery but also for improving residents' understanding of liver anatomy and surgical planning.^{6,9,10} The presentation of these 3D models is mostly as 3D PDFs on 2D screens and, therefore, it still has the limitation of depending on the viewer's mental ability to reconstruct images into 3D structures. In light of recent developments in digitalization of the healthcare system and surgical education, affordable VR solutions have been introduced for reviewing 3D models. Recently, immersive VR environments with context-sensitive presentation integrating relevant patient data have been introduced as a possible solution to improve surgical training and preoperative liver surgery planning.¹¹⁻¹³ While these studies provide subjective data on the potential of VR to enhance complex cognitive skills training, objective data to demonstrate its effectiveness as it relates to high judgmental skills are lacking.

1.3 Hypotheses

- We hypothesize that an immersive VR experience is superior to 3D imaging reconstruction to understand the complex liver anatomy and to devise precise pre-operative planning for general surgery residents.
- We hypothesize that a stepwise training model will enable general surgery residents to understand liver anatomy, surgical approach to liver tumors and pre-operative evaluation of patients.

2. Material and Methods

2.1. Training and assessment methods

- Basic cognitive training: by means of 3 web-based learning modules.
- Three-dimensional anatomy training and operation planning: by means of 3D modeling for planning liver surgery (Synapse 3D workstation vs Immersive VR environment)
- Assessment: by means of MCQs and real case scenarios

2.2. Basic cognitive training

Module 1. Liver anatomy

Module 2. Surgical approach to liver tumors

Module 3. Pre-operative evaluation

2.3. Three-dimensional anatomy training and decision making

The trainees will be trained individually by an investigator in order to be able to interact with 3D software and VR environment. To orient them to the technology and allow them to learn how to manipulate the model, a sample 3D model will be provided in both environments. The familiarization will be considered enough if they can perform the following features independently:

- Rotating of 3D model 360 degrees in both vertical and horizontal axes.
- Making the liver surface transparent to show the intrahepatic structures in relation to the liver surface.
- Isolating each intrahepatic structure to better analysis their configuration.
- Labeling all the structures (portal vein, hepatic artery, hepatic vein, tumor).
- Volumetry of liver base on portal branches.
- Virtual hepatectomy based on portal branches.
- Virtual hepatectomy using extract scoop region (wedge resection).
- Decision-making based on reviewed data

2.4. Assessment tools

1. A validated multiple choice questionnaire (MCQ) will be used to test whether residents will acquire the appropriate cognitive knowledge.

Proficiency level is defined as 80% of the average expert score (≥ 12 of 15-MCQs correct).

2. Ten real patient cases will be used as an assessment tool to test whether residents will acquire the appropriate skills in clinical decision making.

Proficiency level is defined as 80% of the average expert score (≥ 8 of 10 cases correct).

2.5. Study population

All surgical residents at Ghent University, Belgium, and Federico II University, Naples, Italy, irrespective of their postgraduate level (1-6), will be invited to participate in the program. Participation of residents will be on voluntary basis, and they are free to withhold their data from the research data set.

2.6. Sample size calculation

For alpha of 0.05, power of 0.80, an estimated standard deviation of 0.6, and moderately expected effect size that is compatible with pooled analysis of previous studies comparing VR with other digital training environments,¹⁴ a sample size of 46 trainees is required to be able to show a statistically significant difference in results. Considering a potential dropout rate of 10%, a total sample size of 50 participants is needed.

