2.7. Statistical analysis

Data analysis will be performed using R version 3.6.1 (2019, The R Foundation for Statistical Computing). Categorical data will be presented as absolute frequency and associated percentage rate. Symmetrically distributed data will be presented as mean \pm standard deviation (SD). For independent samples, t-Test or Mann-Whitney U test, and for dependent samples, paired t-Test or paired Wilcoxon signed-rank test will be used to compare the performance differences according to the type and distribution

of variables. Reckoning with the study's crossover design, the comparison of continuous outcomes will be conducted using a linear mixed model, which assumes treatment (VR vs DI-based training) and period as fixed effects and resident as a random effect. To evaluate the risk of a carryover and learning effect between two sequences of tests, an interaction term *treatment x period* will be included in the mixed model to test for the presence of a carryover effect. Finally, the influence of resident gender and level (senior vs junior) on the outcomes will be explored by including in turn these variables into the model as fixed effects. An α level of $P < .05$ will be considered statistically significant and P values will be calculated 2-sided.

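### Enrolling 50 residents does not cover 10% dropout: it leaves 45, one short of the 46 the plan requires

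*Combined protocol and SAP*

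**What the plan says.** The sample size paragraph (section 2.6) starts from conventional settings, "For alpha of 0.05, power of 0.80", with "an estimated standard deviation of 0.6" and an effect described as moderate but given no numerical value. From these it concludes that "a sample size of 46 trainees is required to be able to show a statistically significant difference in results". It then adds the dropout allowance: "Considering a potential dropout rate of 10%, a total sample size of 50 participants is needed". It gives neither the inflation formula nor a rounding rule.

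Two other sections bear on the point. Section 2.7 states that "P values will be calculated 2-sided". Section 2.8 allocates residents 1:1 to two assessment sequences, so an even total is the natural choice.

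**The concern.** A dropout allowance has one purpose: the number enrolled, less the expected losses, should be at least the number the power calculation needs. Here the enrolment figure fails that test against the requirement and the dropout rate given in the same paragraph.

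Losses are plausible in this trial. Participation is voluntary and residents may withhold their data (section 2.5). They must also reach a benchmark score on the multiple-choice test, with one month for the modules and tests, before they move on to the crossover assessment (section 4). What is at stake is modest: a stated planning figure that does not do what it says, and power slightly below the nominal 80%.

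**Working it through.** **Inputs, all from section 2.6 unless noted**

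- Evaluable residents required: 46
- Dropout rate: 10%
- Stated enrolment: 50
- Alpha 0.05 (two-sided, section 2.7), power 0.80, SD 0.6
- Numerical effect size: not given

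**Can 50 be reproduced?** Only by a shortcut with truncation. Multiplying by one plus the dropout rate gives 46 × 1.10 = 50.6. Rounded up, or to the nearest whole number, that is 51. It becomes 50 only if the fraction is dropped.

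**What 50 delivers.** At 10% dropout: 50 × 0.90 = 45, one fewer than 46. The dropout that 50 can absorb is 1 − 46/50 = 8.0%, or 4 residents.

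**What is needed.** The enrolment N must satisfy N × (1 − 0.10) ≥ 46, so N ≥ 46/0.90 = 51.1.

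| Enrolled | Expected evaluable at 10% dropout | Meets 46? |
|---|---|---|
| 50 | 45.0 | no |
| 51 | 45.9 | no |
| 52 | 46.8 | yes |

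The answer is 52, which also splits evenly into 26 per sequence.

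**Cost in power.** The plan gives no numerical effect, so I set the effect at the value for which 46 residents give exactly 80% power. With a normal approximation for a paired comparison, the standardised effect is (1.960 + 0.842)/√46 = 0.413. Power at 45 is then Φ(0.413 × √45 − 1.960) = Φ(0.811) = 79.1%. A paired t-test and a two-group t-test calibrated in the same way also give 79.1%.

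As a second check, I assumed a difference of 0.5 with SD 0.6. The two-group normal formula gives 2 × (1.960 + 0.842)² × 0.6²/0.5² = 22.6, so 23 per group and 46 in total. This matches the plan's base figure, but the 0.5 is my assumption. On that basis power is 80.7% with 46 and 79.8% with 45, again a loss of about 0.9 points.

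**Chance of falling short.** If each resident drops out independently with probability 10% (an assumption), the probability of at least 46 completers is 0.431 with 50 enrolled and 0.739 with 52. The chance of ending below 46 is therefore 57% and 26% respectively.

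**The case against.** The best case for leaving the sentence alone is that the discrepancy is trivial. It amounts to one resident and less than one point of power. The plan calls the dropout rate potential, which suggests a rough allowance, and it does not describe 50 as a cap: all surgical residents at two universities are invited, so more may enrol.

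The base of 46 also cannot be confirmed, because no numerical effect is stated. With SD 0.6 and assumed differences from 0.3 to 0.6, a two-group total ranges from 126 down to 32. A paired total, reading 0.6 as the SD of the differences, ranges from 32 down to 8. Against such ranges, 45 versus 46 hardly matters. Finally, restating the allowance as 8% could look like fitting the assumption to the number.

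Much of this stands as a comment on weight. The shortfall is not evidence that the trial is underpowered in any meaningful sense, and 79.1% is conditional on 46 giving 80%. It does not make the sentence correct. The inconsistency lies among three figures in one paragraph and holds whatever effect size lies behind 46. No formula or rounding rule in the documents resolves it, and even the shortcut rounds to 51. Saying that 50 tolerates 8% dropout describes what the number can bear and is not a new forecast. A sponsor who still expects 10% should use one of the other two wordings below.

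**Conclusion.** The point holds. At the plan's own 10% dropout rate, 50 enrolled residents yield 45, not 46, and the enrolment that meets the plan's requirement is 52. The size is small: one evaluable resident, and about 0.9 points of power (80.0% to 79.1%, on the assumption that 46 gives exactly 80%). The arithmetic on enrolment needs no assumption beyond the plan's figures; only the power figure does. This is a minor correction that does not affect the validity of the trial. Whether 46 is the right base for a crossover design is a separate question, not settled here.

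**What to change.** Correct the last sentence of section 2.6 in one of three ways:

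1. Keep 50 and state that it allows for 8% dropout, leaving 46 evaluable.
2. Keep 50 and 10%, and state that 45 evaluable residents are expected, with power of about 79% on the assumption that 46 gives 80%.
3. Keep 46 and 10%, and raise the enrolment target to 52 (26 per sequence).

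The first two change only the wording and need no extra enrolment. The third adds two residents. Whichever is chosen, give the formula, required number divided by one minus the dropout rate and rounded up, so that a reader can check it.

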2.7. Statistical analysis

Data analysis will be performed using R version 3.6.1 (2019, The R Foundation for Statistical Computing). Categorical data will be presented as absolute frequency and associated percentage rate. Symmetrically distributed data will be presented as mean \pm standard deviation (SD). For independent samples, t-Test or Mann-Whitney U test, and for dependent samples, paired t-Test or paired Wilcoxon signed-rank test will be used to compare the performance differences according to the type and distribution

of variables. Reckoning with the study's crossover design, the comparison of continuous outcomes will be conducted using a linear mixed model, which assumes treatment (VR vs DI-based training) and period as fixed effects and resident as a random effect. To evaluate the risk of a carryover and learning effect between two sequences of tests, an interaction term *treatment x period* will be included in the mixed model to test for the presence of a carryover effect. Finally, the influence of resident gender and level (senior vs junior) on the outcomes will be explored by including in turn these variables into the model as fixed effects. An α level of $P < .05$ will be considered statistically significant and P values will be calculated 2-sided.

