2.8. Randomization

Using computer-generated randomization stratified by postgraduate (PG) level (Junior (PG 1-2) vs Senior (PG ≥ 3)) and institution, residents will be randomized in a 1:1 allocation to one of two assessment sequences to devise a surgical plan for 10 clinical scenarios. In group A, the first five cases will be evaluated via a DI, and the second five cases will be evaluated in the VR environment; while in group B, the sequence of cases will be reversed. We consider one-hour washout time between the first and the second sequence of cases.

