3.1. Primary outcome

- The difference in accuracy of the residents' decision-making when reviewing patient data along with 3D liver models visualized via DI or VR, measured by comparing their performance to experts' opinion.

3.2. Secondary outcomes:

- Percentage of residents achieving proficiency in clinical decision-making after completing the training curriculum
- The difference in the timing to devise treatment plans using DI or VR
- Percentage of correct anatomical landmark and liver segments identification using DI or VR
- Knowledge retention assessed by comparing MCQs score before and after e-learning training

4. Cross-over randomized trial

After signing informed consent, all participants will complete a pre-training questionnaire to determine their demographic information and their experience in liver surgery. Then, they will answer a set of 15 MCQs to assess their baseline cognitive knowledge. Subsequently, they will receive the 3 e-learning models to study. After completion of e-

learnings, 15-MCQ will be provided. When the average MCQ score (i.e. at least 80%) of the experts (benchmark) has been achieved, they can progress to the next training step. If they will not accomplish the required score, they are referred to the e-learning platform and once they feel ready, a second different set of MCQ should be completed until they reach the benchmark score. They will have one month time to study the modules and associated tests on their own pace.

For the next step, residents will be invited to an individualized training session for 3D anatomy training and clinical decision-making. Participants will be trained individually by an investigator to be able to interact with SYNAPSE VINCENT and LiVeR Trainer. After completing the training session, the two groups will be compared for accuracy of their surgical planning when they used DI or VR to review 3D models of liver during surgical planning. Group A will receive the first 5 cases along with 3D models via DI and the second 5 cases in the VR environment, while group B will receive a reverse sequence of cases.

5. Ethics

The institutional review board at Ghent University Hospital reviewed and approved the protocol (IRB approval No. B6702020000275). Participation of trainees will be voluntary and informed consent will be obtained from all of them.

6. References

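### Section 2.7 covers the DI-versus-VR accuracy comparison by two overlapping rules, paired tests and a period-adjusted mixed model, without saying which is primary, and the paired tests ignore period

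*Combined protocol and SAP*

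**What the plan says.** Section 2.7 gives two rules that can each take the accuracy comparison.

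- Simple tests: unpaired tests for independent samples; "for dependent samples, paired t-Test or paired Wilcoxon signed-rank test will be used to compare the performance differences according to the type and distribution" of the variable.
- Mixed model: in view of the crossover, "the comparison of continuous outcomes will be conducted using a linear mixed model", with treatment and period fixed, resident random, and a treatment-by-period interaction to test for carryover.

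Section 3.1 defines the primary outcome as the difference in decision accuracy between DI and VR, judged against expert opinion. It names no test and does not say whether accuracy is a count, a proportion or a continuous score. Section 2.4 scores the ten cases as correct or not, and Section 2.8 gives each tool five cases, so a 0-5 count per tool is the natural reading.

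Section 2.8 says that in group A "the first five cases will be evaluated via a DI, and the second five cases will be evaluated in the VR environment", and that the sequence of cases is reversed in group B. Section 4 says that "the two groups will be compared for accuracy of their surgical planning when they used DI or VR".

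**The concern.** DI and VR scores from one resident are dependent, so the paired-test rule applies. If the score is treated as continuous, the mixed-model rule applies too. A reader who does not regard a 0-5 count as continuous would go to Wilcoxon, and nothing in the text forbids it.

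The choice matters because only the mixed model contains period. The ten plans in Section 2.9 run from left lateral resection to central hepatectomy and unresectable tumors. No balancing of difficulty between the two sets of five is described, and Section 2.7 itself foresees a learning effect. A period difference is therefore plausible. At stake are the power and error rate of the primary test and, if completers are unequal, its estimate.

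**Working it through.** **1. Does the sample size show which analysis was meant?** Section 2.6 gives "For alpha of 0.05, power of 0.80, an estimated standard deviation of 0.6"; Section 2.7 says "P values will be calculated 2-sided". The effect is described only as a "moderately expected effect size that is compatible with pooled analysis of previous studies", with no number. Using (1.960 + 0.842)² = 7.85:

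- Unpaired, assumed difference 0.5: 2 × 7.85 × 0.36 / 0.25 = 22.6, so 23 per group, 46 in total.
- Paired, assumed difference 0.25 and 0.6 taken as the SD of differences: 7.85 × 0.36 / 0.0625 = 45.2, so 46.

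Both reproduce 46, so the sample size does not settle the question.

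**2. What a period effect does to a paired test.** Let τ be the VR effect and π the mean of period 2 minus period 1. VR minus DI has mean τ + π in group A (VR second) and τ − π in group B (VR first).

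- Mean paired difference = τ + π(nA − nB)/N, which is τ when the sequences are equal.
- With equal sequences, the variance used by the paired test is about σd² + π², although the true sampling variance of the mean needs only σd². The test is therefore too conservative.
- Period-adjusted estimate = [(τ + π) − (π − τ)]/2 = τ, whatever the sequence sizes.

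**3. Continuous score.** Take SD 0.6 and an assumed within-resident correlation of 0.5, so σd² = 2 × 0.36 × 0.5 = 0.36 and σd = 0.6. With τ = 0.25 and N = 46, τ/SE = 0.25 × √46 / 0.6 = 2.83.

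- π = 0.3: the paired test's SD is √(0.36 + 0.09) = 0.671, so the effective critical value is 1.96 × 0.671/0.6 = 2.19. Type I error is about 0.028.
- π = 0.6: the SD is √0.72 = 0.849 and the critical value 2.77. Type I error is about 0.006.

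Simulation (20,000 runs per setting, 23/23) agrees: type I error 0.029 and 0.006. Simulated power of the paired t-test is 0.79, 0.72 and 0.49 at π = 0, 0.3 and 0.6, against about 0.79 throughout with period adjustment. At τ = 0.5 the loss is under 2 points.

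**4. Score of 0-5 per tool.** Assumed logistic model: resident SD 0.7, case spread ±0.6, VR log-odds 0.6 (about 11 percentage points), 23/23. Set success rates are averages over residents and cases. The period-adjusted analysis is a two-sample t-test on period differences, which with complete data gives the same treatment test as the mixed model without the interaction.

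| Set success | Period-adjusted | Paired t | Wilcoxon |
|---|---|---|---|
| 75% vs 55% | 0.74 | 0.59 | 0.58 |
| 70% vs 60% | 0.77 | 0.74 | 0.73 |
| equal | about 0.76 | about 0.76 | about 0.76 |

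At 75% vs 55% without a VR effect, paired type I error is about 0.015. If 75% and 55% instead describe a median resident on a middling case, power is 0.76, 0.64 and 0.61.

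**5. Unequal completers, 75% vs 55%.** By step 2 with π of about −20 points, the shift is −20 × 5/45 = −2.2 points at 25/20 and +2.2 at 20/25. Simulation gives a paired estimate of 8.7 against 10.7 adjusted, and 12.6 against 10.5.

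**6. Does period stand for case set?** The reversal in group B can be read in two ways.

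- Cases 1-5 by VR, then 6-10 by DI: case set coincides with period, and the period term absorbs it.
- Cases 6-10 by VR, then 1-5 by DI: in both groups cases 1-5 are always seen by DI and 6-10 by VR. Case set is confounded with tool, and no listed analysis separates them.

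**7. The interaction.** In a two-period, two-sequence design with ordinary dummy coding, adding treatment by period turns the treatment coefficient into the effect in one period, a comparison between groups. At τ = 0.25 an unpaired period-1 comparison has simulated power of about 0.28, against 0.79.

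**The case against.** The best defence is that the mixed-model sentence opens by invoking the crossover and carries all the period, carryover and subgroup terms, so it is probably the intended primary analysis, with the simple tests left for comparisons such as MCQ scores before and after e-learning. That is likely the intent, but the text does not say so, and its restriction to continuous outcomes leaves a count score in doubt. It is also fair that the documents give no case-set difficulty: the loss is small at 70% vs 60% and absent with equal sets.

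Three stronger readings are tempting but not supported.

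- *Unpaired tests, paired tests and the mixed model all apply at once.* Unpaired tests are limited to independent samples, which DI and VR scores from one resident are not. Only the loose between-group wording in Section 4 points that way, and that sentence goes on to the two tools.
- *The paired analysis is biased in general.* With equal sequences the period effect cancels. A shift needs unequal completers and can go either way.
- *Choosing among tests inflates type I error.* Taking the smallest of five p-values would give about 6% to 9%, but the plan selects by type and distribution. A rule that tests normality first and then picks Wilcoxon or paired t had type I error of 0.014 to 0.053 in the settings tried.

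**Conclusion.** The point holds as an unresolved overlap: the primary accuracy comparison falls under two rules, one of which ignores period. Under an assumed 20-point gap between case sets, the paired tests give up about 15 points of power (0.59 or 0.58 against 0.74) and run at a type I error near 0.015. The loss shrinks to about 4 points at a 10-point gap and to nothing with equal sets. The shift in the estimate is about 2 points, of either sign, at a 25/20 or 20/25 split, and zero with equal sequences.

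These sizes rest on assumed set difficulty, VR effect and resident variation, on accuracy being scored 0-5 per tool, and on both groups seeing the same five cases first. Since period adjustment costs essentially no power when the sets are equal, the case for fixing it in advance does not depend on the exact figures.

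**What to change.** - **Section 2.7:** name the mixed model with treatment and period as fixed effects and resident as random effect as the single primary analysis of the per-tool accuracy score, whatever its distribution. Test the treatment-by-period term in a separate model, so that it does not change the primary treatment estimate.
- **Section 2.7, simple tests:** limit them to comparisons outside the crossover, such as MCQ before versus after, or label them sensitivity analyses. If a rank check is wanted, compare period differences between sequences with a rank test.
- **Section 4:** say that DI and VR are compared within residents, adjusted for period.
- **Section 2.8:** state that both groups see the same five cases first, so that period absorbs case set. If group B in fact sees the second five first by VR, wording cannot repair the confounding with tool.

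The cost is wording only, provided the case order is as assumed. The downside is that a linear model for a 0-5 score is approximate.

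### The main mixed model omits both stratification factors (PG level and institution); the VR-DI contrast is unaffected, but the planned carryover test loses precision if they are prognostic

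*Combined protocol and SAP*

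**What the plan says.** Section 2.8 describes "computer-generated randomization stratified by postgraduate (PG) level (Junior (PG 1-2) vs Senior (PG ≥ 3)) and institution", with 1:1 allocation to two sequences and a one-hour washout between them. Section 2.7 gives the crossover model for continuous outcomes as "treatment (VR vs DI-based training) and period as fixed effects and resident as a random effect". It adds a treatment-by-period interaction that "will be included in the mixed model to test for the presence of a carryover effect". In a closing exploratory step, gender and level are each added to the model separately. Institution is not mentioned anywhere in section 2.7, although section 2.5 recruits from two universities. The section does not state the contrast coding, does not say whether the interaction stays in the model that yields the primary estimate, and attaches no action to the carryover result.

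**The concern.** An analysis normally carries the factors by which the trial was randomised. In a crossover it is natural to leave them out, because a resident's level and institution are the same in both periods and drop out of the within-resident comparison. That reasoning covers the VR-DI contrast but not every test planned in section 2.7. The carryover test compares residents in one sequence with residents in the other, so differences in seniority and institution add to its error.

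That test is the plan's only formal check on carryover and learning after a one-hour washout. If level and institution predict accuracy, leaving them out makes a weak check weaker. Prognostic value is plausible: residents range from PG 1 to 6 at two universities, and all cases come from one of the two hospitals. Its size is unknown, and the MCQ threshold that residents must pass before the assessment could reduce it.

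**Working it through.** **Inputs.** From the documents: 46 residents before dropout and 10% dropout (2.6), two sequences at 1:1 and two stratification factors (2.8), two-sided 5% tests (2.7). Assumed, because the documents give no value: total variance set to 1, intraclass correlation ICC of 0.3-0.7, and a share R² of between-resident variance explained by the two factors of 10-50%.

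**The plan's own figure.** The 46 cannot be derived from the stated inputs alone, since section 2.6 gives "an estimated standard deviation of 0.6" but no numerical effect. With an assumed raw difference of 0.5, the two-sample formula gives 2 × (1.960 + 0.842)² × 0.6² / 0.5² = 22.6, so 23 per group and 46 in all. Differences of 0.3, 0.4 and 0.6 would give 126, 72 and 32. The figure serves here only as the number of residents, and nothing below changes it.

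**What each term estimates.** Write A1 (DI) and A2 (VR) for the period means in group A, and B1 (VR) and B2 (DI) for group B.
- Interaction: (A2 − B2) − (B1 − A1) = (A1 + A2) − (B1 + B2). This is the sequence difference in resident totals, a between-resident contrast.
- Treatment effect without the interaction, complete data: [(A2 − A1) − (B2 − B1)] / 2. This uses only within-resident changes, so level and institution cancel.
- Treatment coefficient with the interaction kept and period 1 as reference: B1 − A1, a between-resident first-period contrast. Under sum-to-zero coding it is again the within-resident contrast.

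**Carryover SE, adjusted over unadjusted:** √{[4·ICC·(1 − R²) + 2(1 − ICC)] / [4·ICC + 2(1 − ICC)]}
- ICC 0.3, R² 0.1: √(2.48/2.60) = 0.977
- ICC 0.5, R² 0.3: √(2.40/3.00) = 0.894
- ICC 0.6, R² 0.4: √(2.24/3.20) = 0.837

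This is a fall of 2-16%. At the widest assumption (ICC 0.7, R² 0.5) the ratio is √(2.00/3.40) = 0.767, a fall of 23%.

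For 46 residents, on the scale of resident means, the SE at ICC 0.5 is √[(4/46) × 0.75] = 0.2554 unadjusted. At R² 0.3 it is √[(4/46) × 0.60] = 0.2284 adjusted. Power for a 0.5-SD sequence effect goes from 48% to 57%. Across ICC 0.3-0.7, adjusted power is 47-65% when R² is 10-50%. With R² of zero, power is 44-54% with or without adjustment.

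**Treatment SE without the interaction.** With complete data it is √[2(1 − ICC)/46], which contains no between-resident variance, so the ratio is 1.000 (for example 0.1474 at ICC 0.5). Generalised least squares with 50 residents and 10% missing period 2 gives ratios of 0.9994 to 0.9955 (at ICC 0.5 and R² 0.3, 0.1470 becomes 0.1467).

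**First-period contrast, if it were used:** √(1 − ICC·R²), from 0.985 (0.3, 0.1) to 0.872 (0.6, 0.4).

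**Type I error of the carryover test.** A simulation used 20,000 runs, 46 residents, four strata and balance forced within strata. Unexplained between-resident variance was 0.35 and within-resident variance 0.5.

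| Level / institution effect | Type I error, unadjusted / adjusted | Power at 0.5, unadjusted / adjusted |
|---|---|---|
| 0 / 0 | 4.9% / 4.9% | 57% / 57% |
| 0.4 / 0.2 | 4.2% / 5.0% | 54% / 57% |
| 0.8 / 0.4 | 2.6% / 5.1% | 44% / 57% |

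With near-equal strata, the second row has R² of about 0.05/0.40 = 12.5% and the third about 0.20/0.55 = 36%.

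**The case against.** The strongest reply is that the primary result is untouched. The VR-DI contrast is within residents, and its estimate and SE are the same with or without the factors. That stands. A reader might infer that the primary comparison is biased or underpowered by the omission, and neither follows.

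A reader might also expect a gain for residents with incomplete data. The direction is right but the size is negligible, below 0.5%. Even this may be generous: the two periods are an hour apart, so dropout is likelier during the month of e-learning, and residents lost then add no outcome data to any model.

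Two further inferences depend on things the documents do not state.
- That the unadjusted carryover SE is too wide for the design. This needs prognostic strata and balance forced within strata, for example by blocking. Section 2.8 mentions stratification but not blocking.
- That the primary treatment coefficient becomes a first-period contrast under R's default coding. Section 2.7 names R but gives no coding, and the interaction reads more naturally as a separate check. If it did stay in the model, adding covariates would not cure the problem; the estimand or coding would have to be specified.

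It is also fair that the carryover gain is assumed and could be zero, that no decision is tied to the test, and that level already enters an exploratory fit. These replies limit the importance of the point. They do not explain why institution, a stratification factor, is in no model.

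**Conclusion.** The mismatch is real: two factors define the randomisation strata, and neither is in the main model. Its effect is confined in practice to the carryover test. That test's SE would be about 2-16% smaller with the factors included, if they explain 10-40% of between-resident variance at an ICC of 0.3-0.6, and no smaller if they are not prognostic. If they are prognostic and balance is forced within strata, the unadjusted test is also conservative (4.2% or 2.6% in place of 5% in the cases simulated). The documents supply neither the ICC nor the prognostic strength, so these figures show a range and do not predict the trial's gain. Severity is low.

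**What to change.** In section 2.7, prespecify PG level (junior/senior, as used for randomisation) and institution as fixed effects in the mixed model, and keep both in the version that contains the treatment-by-period term. State that the primary VR-DI estimate comes from the model without that term, or from the model with sum-to-zero coding, so that it remains a within-resident contrast. The exploratory step can then be limited to gender, with the level effect read from the main model.

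The cost is a few lines of SAP text and two between-resident degrees of freedom. For the carryover test with 46 residents these go from 44 to 42, which moves the critical t from 2.015 to 2.018. Both variables are already collected for randomisation, and the sample size does not change. The SAP should not present the adjusted carryover test as adequate: under the assumptions above its power for a 0.5-SD effect reaches at most about 65%.
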